## 3 Objectives and Endpoints

### **3.1 Objectives**

#### **3.1.1 Primary Objective**

The primary study outcome is kidney damage after cardiac surgery identified by measuring the biomarkers [TIMP-2]\*[IGFBP7] in high risk.

#### **3.1.2 Secondary Objectives**

Secondary objectives include:

- Occurrence of AKI  
The rate of AKI within 72h after cardiac surgery will be evaluated according to the KDIGO guidelines using both serum-creatinine and/or urinary output criteria.
- Occurrence of moderate and severe AKI within 72h after cardiac surgery  
The rate of moderate and severe AKI within 72h after cardiac surgery will be evaluated according to the KDIGO stages 2 and 3 .
- Creatinine clearance on day one after cardiac surgery
- Free days through days 28 of vasoactive medications and mechanical ventilation
- Renal recovery at day 90  
Recovery of renal function will be defined as serum creatinine levels < 0.5 mg/dl higher than baseline (level prior to surgery).
- Mortality at day 30, 60, and 90
- Vasopressor use
- Fluid application and volume status
- ICU length-of-stay AND Hospital length-of-stay  
Both ICU and hospital length-of-stay will be defined based on the ICU and acute hospital admissions during patients' randomization. Length-of-stay will be evaluated on the basis of both the mean number of days of ICU/hospital stay following randomization and Kaplan- Meier survival, censored for patient drop out or death. Hospital discharge will be defined as discharge from acute care, whether to acute rehabilitation, transitional care, long-term care or home.
- Use and duration of renal replacement therapy within 72h after cardiac surgery, and 30, 60 and 90 days after randomization  
The duration of renal support will be defined as the number of days from the initiation of RRT to final dialysis treatment (last data collection 90 days after randomization). Duration of renal support will be censored if the patient is still dialysis dependent at the time of death. Duration of renal support will be evaluated on the basis of both the mean number of days of renal support and Kaplan-Meier survival, censored for patient death. The optimal outcome in AKI is the ability of the patient to return to his or her prior living situation not requiring RRT on an ongoing basis.
- Major adverse kidney events at day 90  
Major adverse kidney event (MAKE) will be defined as the composite of death, use of renal replacement therapy and persistent renal dysfunction (defined as serum

creatinine  $\geq 2x$  compared to baseline value) at day 90.

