	
randomization and [TIMP-2]*[IGFBP7] levels at randomization
 
Secondary Endpoints:
 
 
• occurrence of AKI within 72h after cardiac surgery (according to the KDIGO criteria)
 
• occurrence of moderate and severe AKI within 72h after cardiac surgery (according to the KDIGO stage 2 and 3)
 
• amount of volume application
 
• transient (<72h) and persistent (<72h) AKI
 
• fluid status
 
• dose and duration of vasopressor use
 
• creatinine clearance on day one after cardiac surgery
 
• free-days through day 28 of vasoactive medications and mechanical ventilation
 
• renal recovery at day 90 (renal recovery is defined as serum creatinine levels < 0.5 mg/dl higher than baseline serum creatinine (creatinine level before surgery)
 
• 30-day, 60-day and 90-day mortality
 
• length of ICU stay
 
• length of hospital stay
 
• use and duration of renal replacement therapy within hospital stay
 
• use of RRT at days 30, 60, 90
 
• MAKE90 (major adverse kidney events consisting of mortality, dialysis dependency, persistent renal dysfunction (defined as serum creatinine <math>\geq</math> 2x compared to baseline value) at day 90
 
• Effect of ACEi/ARBs use on the AT II effect
 
• Correlation between the severity of hyperreninemia and the AT II effect
 
 
Other variables:
 
 
• Surveillance of vital parameters on ICU
 
• Safety laboratory parameters
 
• Occurrence of thromboembolism
 
• Adverse events
 
 
Add-on study:
 
 
• determination of further biomarkers (e.g. KIM-1, chitinase, NGAL, hyaluronic acid) and anti- and pro-inflammatory mediators (IL-6, IL-10...)
 

Planned Number of Study Centers:	1

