### 3.2.2 Secondary Endpoints

- occurrence of AKI within 72h after cardiac surgery (according to the KDIGO criteria)
- occurrence of moderate and severe AKI within 72h after cardiac surgery (according to the KDIGO stage 2 and 3)
- amount of volume application within 12h after randomization
- fluid status 12h after randomization
- dose of vasopressor use during intervention
- creatinine clearance on day one after cardiac surgery
- free-days through day 28 of vasoactive medications and mechanical ventilation
- renal recovery at day 90 (renal recovery is defined as serum creatinine levels  $< 0.5$  mg/dl higher than baseline serum creatinine (creatinine level before surgery)
- 30-day, 60-day and 90-day mortality
- length of ICU stay
- length of hospital stay
- use and duration of renal replacement therapy within hospital stay
- use of RRT at days 30, 60, 90
- MAKE90 (major adverse kidney events consisting of mortality, dialysis dependency, persistent renal dysfunction (defined as serum creatinine  $\geq 2x$  compared to baseline value) at day 90
- Effect of ACEi/ARBs use on the AT II effect
- Correlation between the severity of hyperreninemia and the AT II effect

Other variables:

- Surveillance of vital parameters on ICU
- Safety laboratory parameters
- Occurrence of thromboembolism
- Adverse events

Add-on study:

- determination of further biomarkers (e.g. KIM-1, chitinase, NGAL, renin, hyaluronic acid and anti- and pro-inflammatory cytokine levels (IL-6, IL-10...), leukocyte functions

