#### Description of the primary efficacy / test accuracy analysis and population

The primary efficacy analysis will include all randomized subjects (full analysis set) and will be performed according to the intent-to-treat principle, i.e. all subjects are analyzed in the group to which they were randomized. Additional sensitivity analyses will be performed according to the per-protocol principle. The effect of AT-II versus control on the biomarker [TIMP-2]\*[IGFBP7] will be estimated with a non-parametric 90% confidence interval of the location shift between the distributions of the biomarker [TIMP-2]\*[IGFBP7] in the AT-II and the control group, respectively.

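### Day-90 renal recovery is defined by serum creatinine alone, so a survivor still on RRT can count as recovered and as a MAKE90 event on the same day

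*Protocol*

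**What the plan says.** Renal recovery at day 90 is a secondary endpoint, defined in three places of the protocol.

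- Section 3.1.2 (Secondary Objectives): "Recovery of renal function will be defined as serum creatinine levels < 0.5 mg/dl higher than baseline", where baseline is the value before the operation.
- Section 3.2.2 (Secondary Endpoints) has the same 0.5 mg/dl margin, "higher than baseline serum creatinine (creatinine level before surgery").
- Section 1.1 (Synopsis): "0.5 mg/dl higher than baseline serum creatinine (creatinine level before surgery").

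None of the three mentions RRT or survival.

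Two other statements in section 3.1.2 bear on this. The composite kidney endpoint at day 90 does include both: "Major adverse kidney event (MAKE) will be defined as the composite of death, use of renal replacement therapy and persistent renal dysfunction". Sections 3.2.2 and 9.5 name its components as mortality, dialysis dependency and persistent dysfunction. The item on duration of RRT describes the best outcome after AKI as a return to the previous living situation, "not requiring RRT on an ongoing basis".

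On analysis, section 12 assigns categorical secondary outcomes to Fisher's exact test or the chi-squared test. It names an analysis population for the primary endpoint, "The primary efficacy analysis will include all randomized subjects (full analysis set"), and one for safety. It names none for renal recovery.

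**The concern.** Serum creatinine reflects kidney function only while the kidneys are doing the clearing. In a patient on dialysis the measured value depends on the treatment, so a value close to baseline is no evidence of recovery. Applied literally, the rule can therefore record a success for a patient with one of the worst renal outcomes in the trial. Such a patient also counts against the same arm in MAKE90, so two endpoints meant to describe the same day-90 kidney status would disagree.

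Death raises a related but weaker point. A patient who died has no day-90 creatinine, and the protocol does not say whether that patient is a non-recovery, is missing, or is outside the denominator. If such patients were treated as missing, the arms would be compared among survivors only, and a difference in mortality could be hidden from this endpoint.

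**Working it through.** The protocol gives no expected rate, power or precision for renal recovery, so there is no planned figure to reproduce. The check sets the definitions side by side and then bounds the size.

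**1. Can one patient be both recovered and a MAKE90 event?** Let B be the pre-surgery creatinine in mg/dl and C the day-90 value.

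- Recovered: C < B + 0.5.
- MAKE90: dead, or on RRT, or C ≥ 2B.

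For a living patient off RRT, both can hold only if 2B ≤ C < B + 0.5, which needs 2B < B + 0.5, that is B < 0.5 mg/dl. With a baseline of 0.5 mg/dl or more, the two creatinine conditions exclude each other. The only remaining overlap is a survivor on RRT with C < B + 0.5. The contradiction therefore comes from the missing RRT condition, not from the two creatinine cut-offs.

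The overlap is feasible in the eligible population. The exclusion for chronic kidney disease applies only below an eGFR of 20 (synopsis) or 30 (section 5.2.2), so patients with a raised baseline can enter, and for them B + 0.5 is a high absolute value.

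**2. How many patients through RRT?** The only RRT rate in the protocol is in section 2.1: 1–2% of cardiac surgery patients require RRT.

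- 64 × 1% = 0.64 and 64 × 2% = 1.28, so about 1 patient in the whole trial.
- That rate covers any RRT. Misclassification also needs RRT at day 90 and a creatinine under the threshold, so at this rate the expected number is lower.
- The trial selects patients with hyperreninaemia who need vasopressors, which pushes the rate upward. At an assumed 5–10%, 64 × 5% = 3.2 and 64 × 10% = 6.4 patients would receive RRT at some point. The same two conditions would then reduce the number misclassified.
- One reclassified patient in an arm of 32 moves that arm's rate by 1/32 = 3.1 percentage points.

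**3. What could deaths do, if left out?** The protocol gives no mortality rate for this population. At an assumed 90-day mortality of 3–8%, 64 × 3% = 1.9 and 64 × 8% = 5.1, so 2 to 5 deaths.

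Take an uneven split of 5 deaths, 4 against 1, with 3 non-recovered survivors in each arm (all counts assumed):

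| Treatment of deaths | Arm with 4 deaths | Arm with 1 death | Difference |
|---|---|---|---|
| Left out | 25/28 = 89.3% | 28/31 = 90.3% | 1.0 point |
| Counted as non-recovery | 25/32 = 78.1% | 28/32 = 87.5% | 9.4 points |

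The choice of rule changes the apparent difference from 1 to 9 points. Fisher's exact test on the second row gives p = 0.51, so neither reading would be significant at this sample size.

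**4. Are the data there?** Section 9.4 records mortality, need of RRT and major adverse kidney events at T10 (day 90). Its list does not name serum creatinine separately, but MAKE90 and renal recovery as now defined both already need it.

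**The case against.** The strongest reply has three parts.

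*Deaths and denominators belong in the statistical analysis plan.* This stands. A reader might infer that deceased patients drop out of the denominator. The protocol does not say so: it is silent, and an analysis plan that is not shown may settle the matter. Death can be raised here only as a point to clarify in the same sentence. The RRT gap is different. The definition of recovery is written out in the protocol three times, and as written it gives a wrong classification.

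*The number affected is tiny.* This largely stands. A reader might infer that dialysis patients will routinely be counted as successes, or that the arm with more dialysis and death will show the higher recovery rate. The documents support neither as an expectation. The 1–2% is any RRT after cardiac surgery, not dialysis at day 90, and a reversal between arms can be produced only with assumed counts.

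*Nothing is really hidden.* Mortality and RRT at days 30, 60 and 90, and MAKE90, are all separate endpoints, so an excess of death or dialysis would show there. That limits the harm. It does not make the recovery rate correct, and a reader of the results could still meet a recovery figure that conflicts with MAKE90.

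**Conclusion.** The creatinine-only definition is a fault in a stated rule. A survivor on RRT at day 90 can be classified as recovered, against MAKE90 and against section 3.1.2's own account of a good outcome. At the protocol's 1–2% RRT rate this probably touches at most about 1 of 64 patients, or about 3 percentage points in one arm. That bound assumes the general cardiac surgery rate applies to this selected population; a higher rate would raise it.

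How deaths are handled is left open rather than wrong. Its effect depends entirely on mortality figures that the protocol does not give.

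This is a minor issue in one of many secondary endpoints. The primary endpoint, a 12-hour biomarker difference, and the sample size do not depend on it.

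**What to change.** Use one sentence in sections 1.1, 3.1.2 and 3.2.2: *renal recovery at day 90 means that the patient is alive, is not on RRT at day 90, and has a serum creatinine less than 0.5 mg/dl above the pre-surgery value; death before day 90 and RRT at day 90 count as non-recovery.*

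State the denominator in the same place: all randomized patients, or only those who developed AKI. The choice matters because a patient who never had AKI meets the creatinine rule without having recovered from anything. Against that, patients with AKI are a group formed after randomization, so a comparison restricted to them loses the protection of randomization.

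The cost is the wording in three places. RRT need and mortality are already recorded at T10, day-90 creatinine is already needed for MAKE90, and the planned test for a binary outcome is unchanged.

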### **9.5 Study Assessments**

- Blood and urine samples for Add-on-Trial

Blood and urine samples will be collected at 4h after CPB and at 0, 12, and 24h after randomization through routinely placed catheters. The samples will be centrifuged and stored immediately at -80°C until measurement of biomarkers (e.g. NGAL, KIM-1). New renal biomarkers will be assessed. For this the samples will be stored not more than 10 years.

- Safety laboratory test

- complete blood count (thrombocytes included),
- potassium-, sodium-, ionized and total calcium levels
- creatinine, creatinine-clearance, BUN and eGFR,
- pH, bicarbonate
- bilirubine,
- CRP
- PCT
- Coagulation parameter (INR, prothrombin time, thrombin time, fibrinogen, antithrombin)
- Acute kidney injury
  - AKI will be defined according to the KDIGO criteria (see 18.1.2)
- Length of hospital stay
  - Cumulative days from hospital admission until hospital discharge
- Length of ICU stay
  - Cumulative days from ICU admission until ICU discharge
- Major adverse kidney events (MAKE)
  - combined endpoint consisting of mortality, dialysis dependency, persistent renal dysfunction (defined as serum creatinine  $\geq 2x$  compared to baseline value) at day 90

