#### Secondary endpoints

Statistical analysis of the pre-specified secondary endpoints will be performed with descriptive and inferential statistical methods. Secondary outcomes will be evaluated and compared between the randomized treatment arms using the following methods. In case of normally or non-normally distributed metric outcomes, Student's t test or the Mann-Whitney U test will be applied, respectively. Categorical outcomes will be analyzed using Fisher's exact test (2x2 tables) or the Chi test (>2x2 tables). Survival data will be analyzed using the Kaplan-Meier method and the log-rank test. Hazard ratios will be estimated based on Cox proportional hazards models after checking the proportional hazards assumption based on the Schoenfeld residuals.

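### Length of stay and RRT duration censor death like drop-out, which overstates live discharge and RRT cessation; separately, length of stay has two time origins

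*Protocol*

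**What the plan says.** Protocol Section 3.1.2 gives two summaries for each endpoint.

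- **ICU and hospital stay:** "the mean number of days of ICU/hospital stay following randomization", and a Kaplan-Meier analysis "censored for patient drop out or death". The end event is spelled out: "Hospital discharge will be defined as discharge from acute care, whether to acute rehabilitation, transitional care, long-term care or home". Death is not on that list.
- **RRT duration:** "the mean number of days of renal support and Kaplan-Meier survival, censored for patient death". The rule for death on dialysis is explicit: "Duration of renal support will be censored if the patient is still dialysis dependent at the time of death".

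Section 12, under secondary endpoints, adds: "Survival data will be analyzed using the Kaplan-Meier method and the log-rank test". Cox models follow for hazard ratios, and metric outcomes get a t test or Mann-Whitney test. No competing-risk method appears, and no rule says how a patient who dies enters a mean.

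Section 9.5 defines the same stays differently. Hospital stay is "Cumulative days from hospital admission until hospital discharge" and ICU stay is "Cumulative days from ICU admission until ICU discharge". Neither definition says what happens if the patient dies before discharge.

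**The concern.** Kaplan-Meier censoring assumes that a censored patient could still have the event later, at the same rate as those still under observation. That can hold for drop-out. It cannot hold for death, after which neither discharge nor coming off RRT is possible. With death censored, 1 minus Kaplan-Meier describes discharge in a hypothetical population without deaths and lies above the proportion who actually leave alive.

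The mean has a different weakness. With no rule for deaths, the plain reading is that a stay or RRT course cut short by death counts at its observed length, so a death before the typical discharge day enters as a short stay.

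At stake is how two secondary endpoints are read. A harmful imbalance in deaths could go unseen in the discharge curve or, in some circumstances, look like faster discharge.

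The time origin is a separate matter. Two clocks for one endpoint leave the variable undefined, and the choice could be made after the data are seen.

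**Working it through.** The protocol gives no expected stay, mortality or event count for these endpoints, so there is no figure to reproduce. Only the sample size (32 per arm, 64 in total, Section 12) and the general RRT rate in cardiac surgery (1–2%, Section 2.1) come from the document. The rest is assumed.

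**Hand example, one arm of 32.** Assume survivors are discharged on day 12.

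- Each death on day 3 changes the mean by (3 − 12)/32 = −0.28 day. Three deaths change it by 3 × (−9/32) = −0.84 day.
- Each death on day 30 changes it by (30 − 12)/32 = +0.56 day. The sign depends on when deaths occur.
- With three deaths on day 3, 29 patients are at risk on day 12 and all 29 are discharged. Kaplan-Meier falls to 0, so 1 minus Kaplan-Meier is 100%. Actually discharged alive: 29/32 = 90.6%; never discharged: 3/32 = 9.4%.

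**Simulation, 400,000 patients per scenario.** Assumed would-be stay: gamma with mean 9 days in 75% of patients and 22 days in 25%. Deaths fall between days 0.5 and 5, either unrelated to would-be stay or confined to the long-stay group. Would-be stay is the same in every scenario.

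| Deaths | Raw mean (days) | 1 − Kaplan-Meier, day 21 | Discharged alive, day 21 |
|---|---|---|---|
| None | 12.3 | 87.0% | 87.0% |
| 5%, unrelated | 11.8 | 86.9% | 82.8% |
| 10%, unrelated | 11.3 | 87.0% | 78.7% |
| 20%, unrelated | 10.3 | 87.0% | 70.4% |
| 5%, long-stay | 11.3 | 88.8% | 84.4% |
| 10%, long-stay | 10.3 | 90.8% | 81.8% |
| 20%, long-stay | 8.4 | 95.5% | 76.7% |

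The last column is the cumulative incidence of live discharge with death as a competing event. Three things follow.

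1. Whenever there are deaths, 1 minus Kaplan-Meier exceeds the proportion discharged alive.
2. It rises with more deaths only when those who die would have stayed long. Otherwise it stays flat and the deaths are invisible in it.
3. The cumulative incidence falls with more deaths in every scenario.

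**RRT.** Expected patients on RRT: 64 × 0.01 = 0.64 to 64 × 0.02 = 1.28. Chance of none: 0.99^64 = 53% to 0.98^64 = 27%. At an assumed 10% in this higher-risk group, 64 × 0.10 = 6.4 patients.

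**Time origin.** Sections 8.1 and 9.2 place randomization after the renin result 4 hours after bypass. Counting hospital stay from admission therefore adds any pre-operative days, the operation and those hours. For ICU stay the gap is probably hours, since Section 9.2 lists ICU transfer in the same visit as randomization.

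**The case against.** The strongest reply is that the between-arm comparison is sound. Log-rank and Cox with death censored compare cause-specific hazards of discharge, an accepted quantity when death competes. That stands. The error lies in reading 1 minus Kaplan-Meier as the proportion discharged alive or off RRT.

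A second reply concerns direction. A reader might infer that both summaries always reward the arm with more deaths. The documents do not support this, because they give no mortality rate, timing of deaths or length of stay. The curve improves only if those who die would have stayed longest, and a late death lengthens the mean. Section 2.1 links vasoplegia to both higher mortality and longer hospital stay, which makes such dependence plausible but does not establish it.

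Third, the effect is small beside the noise. With an assumed SD of 8 days, the standard error of a difference in means is 8 × √(2/32) = 2.0 days, so an artefact of 0.84 day is under half a standard error. This too stands. So does the point that mean stay is a legitimate descriptive measure of resource use, and that ranking deaths worst would change the endpoint.

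Fourth, on the time origin, 1:1 randomization balances pre-randomization days in expectation, and Section 9.5 could be read as an assessment definition beside an analysis definition. The first part stands. The second does not remove the need to say which clock produces the reported endpoint.

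The point is not one to leave to an analysis plan: the protocol itself fixes the censoring rule and states both origins.

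**Conclusion.** The concern holds in a limited form. Under the rule in Section 3.1.2, 1 minus Kaplan-Meier overstates live discharge and RRT cessation whenever patients die first. At day 21 the excess for discharge was 87.0 − 78.7 = 8.3 and 90.8 − 81.8 = 9.0 percentage points in the two scenarios with 10% early deaths. These sizes rest wholly on the assumed stays and death times; the existence of the excess does not. The shift in the mean also assumes that stays ended by death are counted as observed.

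The two time origins are a genuine inconsistency, but a reader should not infer that they cause or worsen the effect of deaths. They add time that treatment cannot affect, which is noise and not bias.

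The impact on the trial is modest. These are secondary endpoints in a feasibility trial with a biomarker primary endpoint, mortality and MAKE90 are reported separately, and few patients are likely to need RRT. It should be corrected because the text prescribes a misleading summary and the correction is cheap.

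**What to change.** - Use randomization as the single origin for ICU and hospital stay in Sections 3.1.2 and 9.5.
- Estimate live discharge and RRT cessation with cumulative incidence functions treating death as a competing event. Censor only for loss to follow-up and the day-90 end of follow-up.
- In Section 12, describe any log-rank or Cox result with death censored as a cause-specific comparison.
- Label mean days as descriptive, and show them with the number of deaths or separately for survivors and non-survivors.

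The cost is wording in three sections. The software is standard and no new type of data is needed: mortality is recorded from T7 to T10, and deaths are serious adverse events with dates. One detail needs a line: Section 9.4 lists length of stay at T9 (day 60) but not at T10. For a patient still in hospital at T9, the text should say whether the discharge date is taken from the hospital record or the stay is censored at that visit.

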### 2.1 Background Information and Rationale

Acute kidney injury (AKI) can be defined by changes of serum creatinine and/or urine output, according to the KDIGO criteria[6]. In cardiac surgery patients, the AKI rate is up to 30%, with 1–2% of patients requiring renal replacement therapy (RRT)[7-9]. Cardiac-surgery associated AKI (CSA-AKI) is associated with increased short- and long-term morbidity and mortality as well as increasing hospital costs[7-9].

Shock after cardiac surgery is associated with increased mortality[10, 11]. Cardiopulmonary bypass (CPB) represents a common clinical setting of sympathetic nervous system activation and cardiovascular instability. Vasoplegia is a form of distributive shock that is characterized by low arterial pressure with reduced systemic vascular resistance and normal or elevated cardiac output[1]. It occurs in 5 to 25% of patients undergoing cardiac surgery. Patients with vasoplegia after cardiac surgery are at higher risk of organ failure, including AKI, and have an increased mortality rate and longer hospital length of stay[2, 3].

Application of norepinephrine is currently considered as the first-line therapy for vasoplegia but all catecholamines have adverse effects, including myocardial ischemia and arrhythmias[4]. In addition, in vasoplegic states, vascular smooth muscle cells may become unresponsive to catecholamines. The underlying mechanisms are complex and include adrenoceptor desensitization, increased nitric oxide synthesis, activation of adenosine triphosphate-sensitive K+ channels, and vasopressin and corticosteroid deficiency[12].

The renin-angiotensin-aldosterone system (RAAS) is a hormone system that plays a central role in regulating blood pressure and fluid, glomerular filtration rate, and electrolyte balance[13, 14]. Renin, a proteolytic enzyme released by juxtaglomerular cells in response to hypotension, decreases sodium delivery to the distal tubule, activates the sympathetic nerve system, and cleaves angiotensinogen to angiotensin (AT)-I which is a precursor of the vasoactive AT-II. The RAAS system is regulated by a biofeedback loop. AT-II generation inhibits renin release, whereas renin levels increase when there is insufficient activation of the AT-II type 1 receptor. Administration of Angiotensin Converting Enzyme (ACE) inhibitors and AT-II receptor blockers and reduced AT-II generation cause a corresponding increase in renin levels.[15, 16]

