### 5.2 Study Population

Patients at high risk for AKI after cardiac surgery with CPB will be identified by hyperreninemia ( $\Delta$ -renin (difference between post- and pre-operation)  $\geq 3.7 \mu\text{U/ml}$  4 h after CPB).

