#### Sample size

The expected median [TIMP-2]\*[IGFBP7] level in the control group is median control=0.84 (Q1=0.35, Q3=1.57) and in the AT-II group median AT-II=0.58 (Q1=0.26, Q3=1.20), based on Meersch et al., Intensive Care Med 2017. A total number of 64 patients will be recruited and a number of 32 patients will be randomized to each of the two treatment arms. With an expected 5% dropout rate, up to 2 patients per treatment arm will be non-evaluable. With a number of n=30 evaluable patients per treatment arm, the location shift between the distributions of the biomarker [TIMP-2]\*[IGFBP7] in the AT-II and the control group can be estimated with an expected precision  $\pm 0.285\text{ng/ml}^2/1000$  (half-width of the 90% confidence interval).

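### RRT duration is defined only for patients who start RRT, so its Kaplan-Meier comparison (and its mean, unless non-users count as 0) is confined to a group selected after randomisation

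*Protocol*

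**What the plan says.** Section 3.1.2 fixes the measure: "The duration of renal support will be defined as the number of days from the initiation of RRT to final dialysis treatment". It also fixes the analysis, in which duration is to be "evaluated on the basis of both the mean number of days of renal support and Kaplan-Meier survival, censored for patient death". Section 12 (Secondary endpoints) says that secondary outcomes are compared between the randomised arms, and names the t test, Mann-Whitney, Fisher, chi-square and log-rank tests.

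No section says what a patient who never starts RRT contributes. Sections 3.1.2, 3.2.2, 9.5 and 12 are silent. The flow chart (Section 1.2) collects a number of RRT days at discharge/day 7 and at day 90, without saying whether a non-user is 0 or missing.

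The only RRT rate is in the background, Section 2.1: "In cardiac surgery patients, the AKI rate is up to 30%, with 1–2% of patients requiring renal replacement therapy (RRT"). The trial population is narrower. Section 5.2 says: "Patients at high risk for AKI after cardiac surgery with CPB will be identified by hyperreninemia", and Section 5.2.1 adds hypotension needing vasopressors. No RRT rate is given for that group.

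The windows also differ. Section 3.1.2 speaks of 72 hours and of days 30, 60 and 90. Section 3.2.2 lists "use and duration of renal replacement therapy within hospital stay".

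**The concern.** A clock that starts when RRT starts has no origin for a patient who never needs RRT. Taken literally, the measure exists only among users. Starting RRT is itself a criterion for KDIGO stage 3 (Section 18.2), so it belongs to the outcome that the treatment is meant to influence. Comparing arms among users is then no longer a randomised comparison.

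Two things are at stake. With few users, an arm may have nobody to compare. With more users, the comparison can be made but is selected on outcome. If treatment prevents the short courses, the remaining courses in that arm are longer on average, and a benefit can appear as a longer duration of RRT. This is separate from the question of how deaths among RRT users are censored.

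**Working it through.** **Inputs.** Arm size, Section 12 (Sample size): "a number of 32 patients will be randomized to each of the two treatment arms". RRT rate p: 1% and 2% from Section 2.1, for cardiac surgery in general. The rates 5%, 10% and 20% are assumptions covering a higher-risk group. The same p is used in both arms, and patients are treated as independent.

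**Step 1: the plan's own figure.** The plan has 30 evaluable patients per arm and 5% dropout: 30 / 0.95 = 31.6, rounded up to 32 per arm, 64 in total. This agrees with the protocol. The protocol gives no figure for RRT duration itself.

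**Step 2: how many patients have a value.**
- Share without a value = 1 − p
- Expected users in the trial = 64p
- P(no user in the trial) = (1 − p)^64
- P(at least one arm has no user) = 1 − [1 − (1 − p)^32]²

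Example at 2%: 0.98^32 = 0.524, and 1 − (1 − 0.524)² = 0.773.

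| RRT rate | No value | Expected users | No user in trial | At least one arm without a user |
|---|---|---|---|---|
| 1% | 99% | 0.64 | 0.526 | 0.924 |
| 2% | 98% | 1.28 | 0.274 | 0.773 |
| 5% (assumed) | 95% | 3.2 | 0.038 | 0.350 |
| 10% (assumed) | 90% | 6.4 | 0.001 | 0.067 |
| 20% (assumed) | 80% | 12.8 | below 0.001 | 0.002 |

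With 30 per arm the last column reads 0.932, 0.793, 0.383, 0.083 and 0.002. With 32 per arm it passes one half where (1 − p)^32 = 1 − √0.5 = 0.293, that is at p of about 3.8%.

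**Step 3: direction, with invented durations.** Suppose the control arm has four users with 3, 3, 3 and 14 days, and the angiotensin II arm has one user with 14 days because the three short courses were prevented.
- Users-only means: 23/4 = 5.75 days against 14/1 = 14.0 days, which favours control.
- Users-only Kaplan-Meier just after day 3: 1 − 3/4 = 25% still on RRT against 100%, which also favours control.
- Mean over all 32 per arm, non-users as 0: 23/32 = 0.72 against 14/32 = 0.44 days, which favours angiotensin II.

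**Step 4: does the reversal depend on the rate?** Suppose half of the control courses last 3 days and half 14 days, and treatment prevents half of the short ones.
- Users-only mean, control: (3·p/2 + 14·p/2) / p = 8.5 days.
- Users-only mean, treated: (3·p/4 + 14·p/2) / (0.75p) = 7.75/0.75 = 10.3 days.
- Mean over all patients: 8.5p against 7.75p, lower under treatment.

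The rate p cancels from the users-only means, so the wrong direction is not a feature of rare events. The rate only decides how often both arms have users to compare.

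**The case against.** **The 1–2% is not this trial's rate.** This stands. A reader might infer that, on the protocol's own figure, about 98% of the trial's patients will have no value and the comparison usually cannot be made. The documents do not support that. The figure describes cardiac surgery in general, and the trial enrols a high-risk subset with no stated rate. The statement that at least one arm is usually empty holds only up to about 3.8%.

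**The two harms belong to different rates.** This also stands. The example in Step 3 has 4 of 32 control patients on RRT, or 12.5%. At 1–2%, both arms have a user in only 8% to 23% of trials (1 − 0.924 and 1 − 0.773), so a reversal could rarely be observed. At 10% or more, it is no longer true that there is usually nobody to compare.

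**Non-users may be scored 0, and that is detail for a statistical analysis plan.** This stands in part. A reader might infer that the protocol excludes non-users from the mean. It does not say so; it leaves the matter open, and scoring them 0 would repair the mean. It would not repair a Kaplan-Meier curve whose clock starts at RRT initiation. That origin is a rule stated in the protocol, and an analysis plan that follows it inherits the fault.

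**Other endpoints guard against misreading.** Use of RRT, RRT at days 30, 60 and 90, and MAKE at day 90 apply to everyone randomised, so fewer users would be visible beside a longer duration. This softens the consequence but does not make the duration comparison valid.

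**Conclusion.** The point holds as a defect in a stated secondary analysis. The Kaplan-Meier comparison of RRT duration is restricted to patients selected after randomisation, and so is the mean unless non-users are scored 0. Both can point the wrong way at any RRT rate if treatment prevents short courses; the documents do not show that they will.

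The size is conditional on the unknown rate in this population. Whether the arms can be compared at all is sensitive to it, while the share of patients without a value stays at 90% or more up to a rate of 10%. These figures assume equal rates in the two arms, and the durations used to show direction are invented.

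The correction should be made, but this is one secondary item in a trial with a biomarker primary endpoint, and no primary conclusion depends on it.

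**What to change.** In Sections 3.1.2 and 3.2.2 (and the matching synopsis entry), make the quantity compared between arms the number of days alive and free of RRT from randomisation through day 90, in all randomised patients. Days after death count as not free, and a survivor who never needs RRT scores 90. Compare arms with the Mann-Whitney test already planned in Section 12. Report the durations among RRT users descriptively, without a test. This follows the pattern of the free-days endpoint through day 28 already in Section 3.1.2.

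Reconcile the observation window between Sections 3.1.2 and 3.2.2 at the same time.

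The cost is wording, plus RRT start and stop dates that the present definition already needs. Section 9.4 allows the day-90 contact 14 days early (day 76), so a rule is needed for patients last seen before day 90.

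The drawback is low power: most patients will tie at 90, and deaths, which are also counted in the mortality endpoints and MAKE, will supply much of the variation. The comparison would nevertheless be a randomised one that includes every patient.
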